#### 8.4.1.2 Hematologic Toxicity at Least Possibly Related to Entinostat

The guidelines in [Table 8-3](#) will be followed for determining the timing of cycles based on hematologic status at the time of planned dosing.

#### 8.4.2 Pembrolizumab

AEs associated with pembrolizumab exposure may represent an immunologic etiology. These immune-related AEs (irAEs) may occur shortly after the first dose or several months after the last dose of pembrolizumab treatment and may affect more than one body system simultaneously. Therefore, early recognition and initiation of treatment is critical to reduce complications. Based on existing clinical study data, most irAEs were reversible and could be managed with interruptions of pembrolizumab, administration of corticosteroids and/or other supportive care. For suspected irAEs, ensure adequate evaluation to confirm etiology or exclude other causes. Additional procedures or tests such as bronchoscopy, endoscopy, skin biopsy may be included as part of the evaluation. Based on the severity of irAEs, withhold or permanently discontinue pembrolizumab and administer corticosteroids. Dose modification and toxicity management guidelines for irAEs associated with pembrolizumab are provided in [Table 8-4](#). (Refer to [Section 8.5.2](#) and the Study Manual for supportive care guidelines, including use of corticosteroids.)

**Table 8-4 Pembrolizumab Dose Modification and Toxicity Management Guidelines for Immune-Related Adverse Events**

General instructions:				
IR AEs	Toxicity Grade or Conditions (CTCAEv4.0)	Action Taken to Pembrolizumab	IR AE Management with Corticosteroid and/or Other Therapies	Monitor and Follow-up
Pneumonitis	Grade 2	Withhold	Administer corticosteroids (initial dose of 1-2 mg/kg prednisone or equivalent) followed by taper	Monitor participants for signs and symptoms of pneumonitis Evaluate participants with suspected pneumonitis with radiographic imaging and initiate corticosteroid treatment Add prophylactic antibiotics for opportunistic infections
	Grade 3 or 4, or recurrent Grade 2	Permanently discontinue		

General instructions:

1. Corticosteroid taper should be initiated upon AE improving to Grade 1 or less and continue to taper over at least 4 weeks.
2. For situations where pembrolizumab has been withheld, pembrolizumab can be resumed after AE has been reduced to Grade 1 or 0 and corticosteroid has been tapered. Pembrolizumab should be permanently discontinued if AE does not resolve within 12 weeks of last dose or corticosteroids cannot be reduced to  $\leq 10$  mg prednisone or equivalent per day within 12 weeks.
3. For severe and life-threatening irAEs, IV corticosteroid should be initiated first followed by oral steroid. Other immunosuppressive treatment should be initiated if irAEs cannot be controlled by corticosteroids.

IR AEs	Toxicity Grade or Conditions (CTCAEv4.0)	Action Taken to Pembrolizumab	IR AE Management with Corticosteroid and/or Other Therapies	Monitor and Follow-up
Diarrhea / Colitis	Grade 2 or 3	Withhold	Administer corticosteroids (initial dose of 1-2 mg/kg prednisone or equivalent) followed by taper	
Monitor participants for signs and symptoms of enterocolitis (ie, diarrhea, abdominal pain, blood or mucus in stool with or without fever) and of bowel perforation (ie, peritoneal signs and ileus).
 
Participants with <math>\geq</math>Grade 2 diarrhea suspecting colitis should consider GI consultation and performing endoscopy to rule out colitis.
 
Participants with diarrhea/colitis should be advised to drink liberal quantities of clear fluids. If sufficient oral fluid intake is not feasible, fluid and electrolytes should be substituted via IV infusion.

	Grade 4	Permanently discontinue		
AST / ALT elevation or Increased bilirubin	Grade 2	Withhold	Administer corticosteroids (initial dose of 0.5- 1 mg/kg prednisone or equivalent) followed by taper	
Monitor with liver function tests (consider weekly or more frequently until liver enzyme value returned to baseline or is stable)

	Grade 3 or 4	Permanently discontinue	Administer corticosteroids (initial dose of 1-2 mg/kg prednisone or equivalent) followed by taper	
Type 1 diabetes mellitus (T1DM) or Hyperglycemia	Newly onset T1DM or Grade 3 or 4 hyperglycemia associated with evidence of $\beta$ -cell failure	Withhold	Initiate insulin replacement therapy for participants with T1DM  Administer anti-hyperglycemic in participants with hyperglycemia	Monitor participants for hyperglycemia or other signs and symptoms of diabetes.

General instructions:

1. Corticosteroid taper should be initiated upon AE improving to Grade 1 or less and continue to taper over at least 4 weeks.
2. For situations where pembrolizumab has been withheld, pembrolizumab can be resumed after AE has been reduced to Grade 1 or 0 and corticosteroid has been tapered. Pembrolizumab should be permanently discontinued if AE does not resolve within 12 weeks of last dose or corticosteroids cannot be reduced to  $\leq 10$  mg prednisone or equivalent per day within 12 weeks.
3. For severe and life-threatening irAEs, IV corticosteroid should be initiated first followed by oral steroid. Other immunosuppressive treatment should be initiated if irAEs cannot be controlled by corticosteroids.

IR AEs	Toxicity Grade or Conditions (CTCAEv4.0)	Action Taken to Pembrolizumab	IR AE Management with Corticosteroid and/or Other Therapies	Monitor and Follow-up
Hypophysitis	Grade 2	Withhold	Administer corticosteroids and initiate hormonal replacements as clinically indicated.	Monitor for signs and symptoms of hypophysitis (including hypopituitarism and adrenal insufficiency)
	Grade 3 or 4	Withhold or permanently discontinue 		
Hyperthyroidism	Grade 2	Continue	Treat with non-selective beta-blockers (e.g., propranolol) or thioamides as appropriate	Monitor for signs and symptoms of thyroid disorders
	Grade 3 or 4	Withhold or permanently discontinue 		
Hypo-thyroidism	Grade 2-4	Continue	Initiate thyroid replacement hormones (eg, levothyroxine or liothyroinine) per standard of care	Monitor for signs and symptoms of thyroid disorders
Nephritis and Renal dysfunction	Grade 2	Withhold	Administer corticosteroids (prednisone 1-2 mg/kg or equivalent) followed by taper	Monitor changes of renal function
	Grade 3 or 4	Permanently discontinue		
Myocarditis	Grade 1 or 2	Withhold	Based on severity of AE administer corticosteroids	Ensure adequate evaluation to confirm etiology and/or exclude other causes
	Grade 3 or 4	Permanently discontinue		

General instructions:

1. Corticosteroid taper should be initiated upon AE improving to Grade 1 or less and continue to taper over at least 4 weeks.
2. For situations where pembrolizumab has been withheld, pembrolizumab can be resumed after AE has been reduced to Grade 1 or 0 and corticosteroid has been tapered. Pembrolizumab should be permanently discontinued if AE does not resolve within 12 weeks of last dose or corticosteroids cannot be reduced to  $\leq 10$  mg prednisone or equivalent per day within 12 weeks.
3. For severe and life-threatening irAEs, IV corticosteroid should be initiated first followed by oral steroid. Other immunosuppressive treatment should be initiated if irAEs cannot be controlled by corticosteroids.

IR AEs	Toxicity Grade or Conditions (CTCAEv4.0)	Action Taken to Pembrolizumab	IR AE Management with Corticosteroid and/or Other Therapies	Monitor and Follow-up
All other IR AEs	Intolerable/persistent Grade 2	Withhold	Based on type and severity of AE administer corticosteroids	Ensure adequate evaluation to confirm etiology and/or exclude other causes
	Grade 3	Withhold or discontinue based on the type of event. Events that require discontinuation include and not limited to: Guillain-Barré Syndrome, encephalitis		
	Grade 4 or recurrent Grade 3	Permanently discontinue		

Withhold or permanently discontinue pembrolizumab is at the discretion of the investigator or treating physician.

**NOTE:**

For participants with Grade 3 or 4 immune-related endocrinopathy where withhold of pembrolizumab is required, pembrolizumab may be resumed when AE resolves to  $\leq$  Grade 2 and is controlled with hormonal replacement therapy or achieved metabolic control (in case of T1DM).

Pembrolizumab may cause severe or life threatening infusion-reactions including severe hypersensitivity or anaphylaxis. Signs and symptoms usually develop during or shortly after drug infusion and generally resolve completely within 24 hours of completion of infusion. Dose modification and toxicity management guidelines on pembrolizumab associated infusion reaction are provided in [Table 8-5](#).

**Table 8-5 Pembrolizumab Infusion Reaction Dose Modification and Treatment Guidelines**

NCI CTCAE Grade	Treatment	Premedication at Subsequent Dosing
Grade 1  Mild reaction; infusion interruption not indicated; intervention not indicated	Increase monitoring of vital signs as medically indicated until the participant is deemed medically stable in the opinion of the investigator.	None
Grade 2  Requires therapy or infusion interruption but responds promptly to symptomatic treatment (e.g., antihistamines, NSAIDs, narcotics, IV fluids); prophylactic medications indicated for $\leq 24$ hrs.	Stop Infusion.  Additional appropriate medical therapy may include but is not limited to:  IV fluids Antihistamines NSAIDs Acetaminophen Narcotics  Increase monitoring of vital signs as medically indicated until the participant is deemed medically stable in the opinion of the investigator.  If symptoms resolve within 1 hour of stopping drug infusion, the infusion may be restarted at 50% of the original infusion rate (e.g. from 100 mL/hr. to 50 mL/hr.). Otherwise dosing will be held until symptoms resolve and the participant should be premedicated for the next scheduled dose.  Participants who develop Grade 2 toxicity despite adequate premedication should be permanently discontinued from further study drug treatment	Participant may be premedicated 1.5h ( $\pm 30$ minutes) prior to infusion of pembrolizumab with:  Diphenhydramine 50 mg po (or equivalent dose of antihistamine).  Acetaminophen 500-1000 mg po (or equivalent dose of analgesic).

NCI CTCAE Grade	Treatment	Premedication at Subsequent Dosing
Grades 3 or 4  Grade 3:  Prolonged (i.e., not rapidly responsive to symptomatic medication and/or brief interruption of infusion); recurrence of symptoms following initial improvement; hospitalization indicated for other clinical sequelae (e.g., renal impairment, pulmonary infiltrates)  Grade 4:  Life-threatening; pressor or ventilator support indicated	Stop Infusion.  Additional appropriate medical therapy may include but is not limited to:  Epinephrine**  IV fluids  Antihistamines  NSAIDs  Acetaminophen  Narcotics  Oxygen  Pressors  Corticosteroids  Increase monitoring of vital signs as medically indicated until the participant is deemed medically stable in the opinion of the investigator.  Hospitalization may be indicated.  **In cases of anaphylaxis, epinephrine should be used immediately.  Participant is permanently discontinued from further study drug treatment.	No subsequent dosing

Appropriate resuscitation equipment should be available at the bedside and a physician readily available during the period of drug administration. For further information, please refer to the Common Terminology Criteria for Adverse Events v4.0 (CTCAE) at <http://ctep.cancer.gov>

Pembrolizumab may be interrupted for situations other than treatment-related AEs such as medical / surgical events or logistical reasons not related to study therapy. Participants should be placed back on study therapy within 3 weeks of the scheduled interruption, unless otherwise discussed with the Sponsor. The reason for interruption should be documented in the patient's study record.

## 8.5 Concomitant Therapy

All concomitant treatments and therapies, or medication, including all prescription, over-the-counter, herbal supplements, and IV medications and fluids, administered during the 30 days preceding the screening study visit must be reported in the electronic case report form (eCRF). If changes occur during the study period, documentation of drug dosage, frequency, route, and date may also be included on the eCRF. The generic name of the drug (or trade name for combination drugs) must be specified along with the route of administration, indication, and duration of treatment.

Throughout the study, the Investigator may prescribe any concomitant medications or treatments deemed necessary to provide adequate supportive care, such as potassium and phosphorus supplements and antiemetics, with the exception of those listed in [Section 8.5.1](#). Patients must notify the Investigator of all concomitant medications taken through completion of the study (final visit).

Medications or vaccinations specifically prohibited in the exclusion criteria are not allowed during the ongoing study ([Section 8.5.1](#)). If there is a clinical indication for any medication or vaccination specifically prohibited during the study, discontinuation from study drug may be required. The Investigator should discuss any questions regarding this with the Medical Monitor. The final decision on any supportive therapy or vaccination rests with the Investigator and/or the patient's primary physician. However, the decision to continue the patient on study drug requires the mutual agreement of the Investigator, the Sponsor, and the patient.

### 8.5.1 Prohibited Medications and Medications to be Avoided During the Study

#### 8.5.1.1. Prohibited Medications

The following medications are prohibited during study participation:

- Any other HDAC inhibitor, including valproic acid
- DNA methyltransferase inhibitors
- Antineoplastic systemic chemotherapy or biological therapy
- Immunotherapy other than pembrolizumab

- Investigational agents other than entinostat and pembrolizumab
- Prophylactic use of hematopoietic colony stimulating factors are not allowed during the Phase 1b Dose Escalation/Confirmation Phase, but can be used to treat hematological adverse events and for prophylaxis subsequently, per investigator discretion during the Expansion Phase.
- Radiation therapy

*Note: Radiation therapy to a symptomatic solitary lesion or to the brain may be considered on an exceptional case-by-case basis after consultation with Sponsor. The patient must have clear measurable disease outside the radiated field. Administration of palliative radiation therapy will be considered clinical progression for the purposes of determining PFS.*

- Live vaccines within 30 days prior to the first dose of study drug and while participating in the study. Examples of live vaccines include, but are not limited to, the following: measles, mumps, rubella, chicken pox, yellow fever, rabies, Bacille de Calmette et Guérin, and typhoid (oral) vaccine. Seasonal influenza vaccines for injection are generally killed virus vaccines and are allowed. However, intranasal influenza vaccines (e.g., Flu-Mist®) are live attenuated vaccines, and are not allowed.
- The use of systemic corticosteroids to treat disease-related complications or co-morbid medical conditions is strongly discouraged. In consultation with the Sponsor, systemic corticosteroids may be administered, at doses no greater than 10 mg prednisone or for no longer than 7 consecutive days if at higher doses, as clinically indicated, to treat acute conditions, (e.g. exacerbations of COPD, pleural effusions, etc.) other than immune-mediated toxicity related to study drug. The corticosteroid regimens used to treat the immune-related toxicity related to study drug are specified in [Section 8.5.2](#).

The use of physiologic doses of corticosteroids for prolonged periods may be approved in consultation with the Sponsor. The use of inhaled steroids for the management of asthma or the use of prophylactic corticosteroids to avoid allergic reactions (e.g., to IV contrast dye) is permitted. Patients who, in the assessment by the Investigator, require the use of any of the aforementioned treatments for clinical management should be removed from the study. Patients may receive other medications that the Investigator deems to be medically necessary.

The exclusion criteria ([Section 6.2](#)) describe other medications that are prohibited in this study.

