#### **12.4.5 Efficacy Analysis**

Efficacy analyses will be conducted using the Full Analysis Set and, where appropriate, the Per-protocol Set.

ORR will be estimated for each cohort evaluated in the Expansion Phase using irRECIST, as the primary endpoint. Crude proportion of patients with best overall response of CR or PR, along with a 2-sided 95% CI, will be calculated for cohorts 1 and 4. The width of the CI will be adjusted to account for the multistage design (Atkinson 1985). Additionally, a 90% one-sided CI of the form  $(\pi_L, 1]$  will be reported since the sample size for the Expansion Phases for cohorts 1 and 4 were determined using a one-sided

significance level of 10%. Crude proportion of patients with best overall response of CR or PR, along with a 2-sided 98% CI, will be calculated for cohorts 2 and 3. CBR at 6 months will be analyzed in a similar manner.

DOOR will be calculated for patients who achieve a CR or PR and is defined as the number of months from the start date of the response (and subsequently confirmed) to the first date that recurrent disease or PD is documented. PFS is defined as the number of months from the date of the first dose of study drug to the earliest of documented PD or death due to any cause without prior progression. OS is defined as the number of months from the first dose of study drug to the date of death due to any cause. DOOR, PFS, and OS will be summarized descriptively using the Kaplan-Meier method with 95% confidence intervals (CIs) calculated using Greenwood's formula. Median follow-up for each endpoint will be estimated according to the Kaplan-Meier estimate of potential follow-up. PFS rate at 6 months and corresponding 95% CIs will be estimated using the Kaplan-Meier method. Greenwood's formula will be used to calculate the standard errors of the Kaplan-Meier estimate and upper and lower limits of the 95% CI.

An analysis of efficacy endpoints also will be performed, with response determined using RECIST, version 1.1.

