3.8 Efficacy Analysis

Efficacy analyses will be performed using the FAS and, where appropriate, the Per-Protocol Set. ORR will be estimated for each cohort evaluated in the Expansion Phase using irRECIST as the primary endpoint. Crude proportion of patients with best overall response of CR or PR, along with a 2-sided 95% CI, will be calculated for each cohort. The width of the CI will be adjusted to account for the multistage design (Atkinson, 1985). Additionally, a 90% one-sided CI of the form $(\pi, 1]$ will be reported for cohort 1 and a 95% one-sided CI will be reported for cohort 4 since the sample size for the Expansion Phases for cohorts 1 and 4 were determined using a one-sided significance level of 10%, 5%, respectively.

Crude proportion of patients with best overall response of CR or PR, along with a 2-sided 92% CI will be calculated for cohorts 2 and 3. ORR based on RECIST 1.1 will be analyzed in a similar manner.

Clinical Benefit Rate

Clinical benefit rate, as determined by irRECIST, will be estimated based on the crude proportion of patients in each cohort whose best overall response during the course of study treatment is a irCR, irPR, or irSD lasting for at least 6 months. Stable disease based on irRECIST will be measured from the start date of study treatment until the criteria for irPD is first met. Approximate 2-sided 95% CIs will be calculated for each cohort. Clinical benefit rate, as determined by RECIST 1.1, will be estimated based on the crude proportion of patients in each cohort whose best response during the course of study treatment is a CR, PR, or SD lasting for at least 6 months. Stable disease based on RECIST 1.1 will be measured from the start date of study treatment until the criteria for PD is first met. Approximate 2-sided 95% CIs will be calculated for each cohort.

Progression-free Survival

The PFS, defined as the number of months from first dose date to PD or death due to any cause, whichever occurs first. Disease assessments will continue until PD, even

after the originally assigned study treatment is discontinued. For purposes of analysis, 1 month is considered 30.4375 days. The duration of PFS as determined by RECIST 1.1 (Eisenhauer 2009) and irRECIST (Seymour 2017) will be summarized descriptively using the Kaplan-Meier method (Kaplan 1958). The PFS at 6 months by irRECIST and RECIST 1.1 will be analyzed in a similar manner.

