The date of progression or censoring for PFS will be determined according to the conventions listed in Table 3-1.

All patients are to be followed for disease progression according to the protocol-specified schedule even after a non-protocol, anti-cancer therapy is started. For the primary analysis of PFS, documented disease progression (or death without prior disease progression) occurring after the start of such therapy will be considered as a PFS event.

Table 3-1. Date of Progression or Censoring for Progression-free Survival

Situation	Date of Progression or Censoring	Outcome
Documented disease progression	Date of disease assessment showing documented disease progression	Progressed
Death without documented progression	Date of death	Progressed
No baseline disease assessments	Date of enrollment	Censored
No post-baseline assessment and no death	Date of enrollment	Censored
Alive and without documentation of disease progression	Date of last disease assessment	Censored
Patient lost to follow-up (or withdrew consent from study participation) before documented progression or death	Date of last disease assessment	Censored

Overall Survival

Overall survival is defined as the number of months from first dose date to the date of death (due to any cause). Patients who are alive or lost to follow-up (as of the data analysis cutoff date) will be censored. The censoring date will be determined from the patients' date of last contact or data analysis cutoff date, whichever date occurs first.

The analysis of OS will be based on the methods described above for PFS. The duration of OS will be summarized descriptively using the Kaplan-Meier method with 95% CIs, calculated using Greenwood's formula.

Duration of Response and Time to Response

Duration of response will be calculated for patients who achieve CR or PR. For such patients, DOR is defined as the number of months from the start date of the PR or CR (whichever response occurs first and subsequently confirmed), to the first date that recurrent disease or PD is documented. The same analysis will be repeated for patients who achieve immune-related CR (irCR) or immune-related PR (irPR). The date of progression or censoring for DOR will be determined according to the conventions listed Table 3-2. These conventions are based on the May 2007 FDA Guidance for Industry, '*Clinical Trial Endpoints for the Approval of Cancer Drugs and Biologics*'. DOR will be summarized descriptively using the Kaplan-Meier method.

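### Protocol 8.5.1.1 counts palliative radiotherapy as progression for PFS, but the protocol's own PFS definition and SAP Table 3-1 do not, and no deviation is declared

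*Protocol*

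**What the plan says.** **Protocol 8.5.1.1 (Prohibited Medications).** Radiotherapy is prohibited on study, with an exception: "Radiation therapy to a symptomatic solitary lesion or to the brain may be considered on an exceptional case-by-case basis after consultation with Sponsor". That same note fixes the consequence for the endpoint: "Administration of palliative radiation therapy will be considered clinical progression for the purposes of determining PFS".

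**Protocol 12.4.5, and the synopsis in matching terms.** The definition opens "PFS is defined as the number of months from the date of the first dose of study drug to the earliest of documented PD or" and closes with death from any cause in a patient who has not already progressed. Neither place mentions radiotherapy or clinical progression.

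**SAP 3.8.** "The PFS, defined as the number of months from first dose date to PD or death due to any cause, whichever occurs first". The criteria are imaging-based: "The duration of PFS as determined by RECIST 1.1" and by irRECIST. Event and censoring dates come from one table: "The date of progression or censoring for PFS will be determined according to the conventions listed in Table 3-1". That table, titled "Date of Progression or Censoring for Progression-free Survival", has six situations, and none of them is radiotherapy or clinical progression. For documented progression the date to use is the "Date of disease assessment showing documented disease progression". SAP 3.8 also follows patients through non-protocol anti-cancer therapy and takes the later documented progression or death as the event.

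**Declaration of departures.** Protocol 12.5 says the SAP will point out where it departs from the protocol's analyses. SAP section 1 says its methods rest on those in the protocol, and its PFS text flags no departure.

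**The concern.** Two rules exist for one situation. The note in 8.5.1.1 ends PFS when palliative radiotherapy is given. The definition and table that a programmer would implement do not. With both rules in force, either could be defended after the data are seen, in an open-label trial with investigator-assessed progression.

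The difference runs in one direction. Following the SAP delays or removes events that 8.5.1.1 counts, so PFS and the 6-month rate look the same or better. Each cohort is single-arm, so no control arm shares the shift and it passes directly into the reported estimate. What is at stake is how two secondary endpoints, PFS and PFS status at 6 months, are read.

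**Working it through.** The plan states no figure for this point. PFS is a descriptive Kaplan-Meier endpoint and the cohort sizes rest on ORR, so there is nothing to reproduce. The check is a comparison of texts, followed by arithmetic for scale.

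**Step 1. One patient under each rule.** Take a patient who receives palliative radiotherapy on study with no documented progression so far.

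| Course after radiotherapy | Protocol 8.5.1.1 | SAP Table 3-1 |
|---|---|---|
| Progression documented later | Event at radiotherapy | Event at the later assessment |
| Death later, no documented progression | Event at radiotherapy | Event at death |
| Alive, or lost to follow-up, no documented progression | Event at radiotherapy | Censored at last disease assessment |

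In no row does the SAP record an event earlier than 8.5.1.1 does.

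**Step 2. Could an existing row absorb the event?** The documented-progression row takes its date from a disease assessment, and SAP 3.8 ties PFS to RECIST 1.1 and irRECIST. Radiotherapy is a treatment, not an assessment under either criterion. Read as a whole, the SAP text does not include it.

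**Step 3. Effect of one reclassified patient on 6-month PFS.** The inputs are the maximum cohort sizes in Protocol 12.1.2. Ignoring censoring, the change is 100/n percentage points:

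- Cohort 1: 100/46 = 2.17
- Cohort 3: 100/52 = 1.92
- Cohort 2: 100/70 = 1.43
- Cohort 4: 100/84 = 1.19

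**Step 4. Plausible total shift.** Let S be 6-month PFS under the SAP, and f the share of patients event-free at 6 months under the SAP who had palliative radiotherapy before then. Under 8.5.1.1 the rate is S × (1 − f), so the shift is S × f. The documents give neither quantity; both are assumed here.

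| S (assumed) | f = 2% | f = 5% | f = 10% |
|---|---|---|---|
| 15% | 0.3 points | 0.75 | 1.5 |
| 25% | 0.5 | 1.25 | 2.5 |
| 40% | 0.8 | 2.0 | 4.0 |

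The low end is less than one patient in any cohort, so it is an average rather than an observable change. The high end is about two patients in Cohort 1 (4.0/2.17 = 1.8) and about three in Cohort 4 (4.0/1.19 = 3.4).

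**Step 5. A note on censoring.** A patient whose last assessment precedes radiotherapy leaves the SAP risk set slightly early. The SAP curve can then sit marginally lower between those two dates, but from the radiotherapy date onward it is at least as high as the curve under 8.5.1.1.

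**The case against.** **The SAP reproduces the formal definition.** A reader might infer that PFS as analysed is not PFS as the protocol defines it. The documents do not support that. The synopsis and Protocol 12.4.5 define PFS by documented progression or death, and the SAP follows them. The radiotherapy rule sits in a note under prohibited medications and was never carried into the protocol's statistical section, so the protocol conflicts with itself as well as with the SAP. This objection stands, and it may explain why no deviation was declared. It does not remove the conflict: the note expressly governs how PFS is determined, and nothing overrides it.

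**Clinical progression might already be captured.** Protocol 11.2.1 lets progression be recorded by clinical disease assessment, and the SAP collects such assessments (2.3.9) and lists them (Listing 16.2.3.15). Radiotherapy recorded that way could arguably enter through the first row of Table 3-1. The stated reliance on RECIST 1.1 and irRECIST points the other way. At best the text is ambiguous, which is itself a reason to settle it.

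**The effect is small.** A reader might infer that if 3-10% of patients were irradiated, 6-month PFS would move by 3-10 points. That would require every one of them to be treated before month 6 and still be free of documented progression at month 6. This is implausible when radiotherapy is allowed only exceptionally, for symptomatic or brain disease, with scans every 6 weeks on a fixed calendar. Where true progression prompted the radiotherapy, the next scan would usually document it, a delay of about one interval. This stands, and the smaller range in the working is the one to use.

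**The SAP's rule is a legitimate choice.** Following patients through later therapy keeps PFS purely imaging-based apart from deaths. That is defensible as a primary analysis, provided it is declared and the other version is shown.

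**Conclusion.** The inconsistency is real and should be fixed, but its consequences are limited. Protocol 8.5.1.1 contradicts the protocol's own PFS definition and SAP Table 3-1, and the departure is undeclared. The SAP version gives PFS and 6-month PFS that are equal or more favourable.

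The likely size is about 0.3 to 4.0 points of 6-month PFS. This rests on the assumed ranges for radiotherapy use and 6-month PFS and ignores censoring. The true frequency may be lower still, since radiotherapy is exceptional.

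A reader might go further and infer that the trial's conclusions are at risk. They are not: PFS is secondary and descriptive, with no test or threshold attached, and sample size, stage decisions and success criteria all rest on ORR.

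**What to change.** Before database lock, reconcile Protocol 8.5.1.1, the synopsis, Protocol 12.4.5 and SAP Table 3-1:

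- Add a row to Table 3-1 making palliative radiotherapy before documented progression a PFS event on the date it starts.
- Carry the same rule into Protocol 12.4.5 and the synopsis. Otherwise the amended SAP would disagree with the formal definition.
- Run one sensitivity analysis that ignores the radiotherapy event.

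If the sponsor prefers to keep the present SAP rule as primary, declare the deviation as Protocol 12.5 requires, and make the analysis that counts radiotherapy as an event the sensitivity run.

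In either case, apply the same choice to PFS at 6 months and state whether it extends to duration of response, since Table 3-2 has no such row either.

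The cost is one table row, matching wording in the protocol and one extra analysis. PFS may come out slightly less favourable. Sample size, alpha and power do not change.
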